1.0 Introduction and Background

Breast cancer changes the lives of more and more women each year. Despite its oncologic benefits, mastectomy results in disfigurement of the chest and women who undergo breast reconstruction demonstrate a profound psychosocial benefit. The outcome of breast reconstruction is highly dependent on the remnant soft tissues and skin after mastectomy. Unfortunately, vascular perfusion-related problems (PRPs) after mastectomy are common and may manifest as skin loss, wound dehiscence, delayed wound healing, or wound/ implant infections. These, in turn, may result in significant patient morbidity as they undergo the process of breast reconstruction. Medications and technologies have been developed to aid in perfusion assessment (fluorescent angiography-FA), perfusion augmentation (nitroglycerin paste-NTG), and wound healing (incisional negative pressure wound therapy-iVAC), but their use and effect in minimizing mastectomy flap skin loss remains unclear.

Indocyanine-green fluorescent angiography (FA) is a safe and efficient technology which implements laser excitation of indocyanine green (ICG) fluorescent dye to provide real-time angiography and assessment of tissue perfusion. Our plastic and reconstructive surgery department and others have utilized FA since it is an accepted technique employed to identify perfusion-related problems in breast and free tissue transfer surgery.

Nitroglycerin ointment exerts a vasodilatory effect on the soft tissue to which it is applied. Thus, nitro paste may help to prevent perfusion-related problems when used in a prophylactic fashion after immediate breast reconstruction. Most recently, a Level 1 evidenced randomized-controlled trial comparing nitroglycerin ointment to placebo in patients undergoing mastectomy with immediate reconstruction has shed new light on the use of this non-invasive treatment to decrease the incidence of potential ischemia-related complications postoperatively.

Vacuum-assisted closure (VAC) dressings, also referred to as negative-pressure wound therapy (NPWT), have been employed since the early 1990's to treat difficult open wounds, and recent evidence has elucidated their role in decreasing complications when placed over surgical closure sites (in which setting they are often referred to as "incisional NPWT" or iVAC). A recent study has demonstrated decreased rates of mastectomy skin flap necrosis when incisional NPWT was placed over the surgical closure compared to no dressing placed over the incision.

2.0 Objectives

Our aim is to evaluate and to compare the above described interventions and their effect on the incidence of PRPs in patients with breast cancer undergoing mastectomy and implant-based immediate breast reconstruction (IBR). The ability to identify, prevent and treat these PRPs can help maximize aesthetic results after breast surgery, improve patient satisfaction with both mastectomy and breast reconstruction, and reduce healthcare cost associated with mastectomy and reconstruction complications.

3.0 Patient Selection

3.1 Inclusion Criteria

The Effect of Nitroglycerin Ointment, Fluorescent Angiography, and Incisional NPWT on Mastectomy Skin Flap Perfusion-Related Problems Comprehensive Cancer Center of Wake Forest University (CCCWFU)

PI: [name] IRB #00038262 NCT03716050 Date of Document: 05/07/2019

- 3.1.1 Patients must be female.
- 3.1.2 Patients must be between the ages of 18 and 99 years.
- 3.1.3 Patients must undergo mastectomy with our attending breast oncology surgeons followed by possible implant-based immediate breast reconstruction (IBR) performed by our attending plastic surgeons at WFBMC.
- 3.1.4 Patients must have the ability to understand and the willingness to sign an IRB-approved informed consent document.

3.2 Exclusion Criteria

- 3.2.1 Patients who are under the age of 18 or over the age of 99.
- 3.2.2 Patients who are undergoing mastectomy without immediate breast reconstruction including immediate breast reconstruction with autologous tissue (or combination of autologous tissue with tissue expanders or implants), or patients with a history of mastectomy presenting for delayed breast reconstruction.
- 3.2.3 Patients with pre-existing conditions in which use of indocyanine-green is contraindicated or must be used with caution, including those with a history of allergy to iodides or iodinated dye, those with chronic kidney disease, those with hepatic failure or cirrhosis of the liver, and females who are nursing, pregnant, or may become pregnant.
- 3.2.4 Pregnant women are excluded from this study because pregnancy precludes immediate breast reconstruction in our patient population.
- 3.2.5 Patients with pre-existing conditions in which use of nitroglycerin paste is contraindicated, including those with a history of cardiac insufficiency, hypotension, sensitivity to nitrites, severe liver impairment, glaucoma, hyperthyroidism, recent head trauma, severe anemia, or taking certain medication (i.e. alteplase, aspirin, beta-blocker, calcium channel blocker, diuretics or thiazides).
- 3.2.6 Patients with pre-existing conditions in whom use of incisional negative pressure wound therapy is contraindicated including those with evidence of surgical site infection (i.e. erythema, purulent drainage), clinical signs of hematoma (i.e. wound swelling, fluctuance, blood drainage), history of persistent cancer, exposed blood vessel on site of proposed therapeutic use, or allergy to acrylics and adhesives.

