4.0 Study Outcomes and Study Measures

We will perform a randomized pilot study comprised of eight groups. All of these groups employ accepted techniques, medications and dressings and therefore are not experimental.

Group 1: Breast skin after mastectomy will be clinically examined by the surgeon to determine if there is adequate blood flow to the skin to allow safe coverage of the breast implant. No dye study, ointment, or vacuum dressing will be applied to the breast after implant placement.

Group 2 - Breast skin after mastectomy will be clinically examined by the surgeon, and nitroglycerin (NTG) cream will be applied to the breast skin after implant placement. This cream does not have systemic effects but may improve blood flow to the remnant breast skin after mastectomy.

Group 3 - Breast skin after mastectomy will be clinically examined by the surgeon, and an incisional vacuum-assisted dressing (iVAC) will be placed over the breast incisions after implant placement, which may improve blood flow to the skin and help wound healing.

Group 4 - Breast skin after mastectomy will be clinically examined by the surgeon, and both NTG cream will be applied to the breast skin and an iVAC will be placed over the incisions after implant placement.

Group 5 - Blood flow to breast skin after mastectomy will be examined using a fluorescent dye study called fluorescent angiography (FA) to determine if there is adequate blood flow to the skin to allow safe coverage of the breast implant. No further intervention will be used after implant placement.

Group 6 - Blood flow to breast skin breast skin will be examined using FA, and NTG cream will be applied to the skin after the implant is placed.

Group 7 - Blood flow to breast skin breast skin will be examined using FA, and an iVAC will be placed over breast skin incisions after the implant is placed.

Group 8 - Blood flow to breast skin breast skin will be examined using FA, and both NTG cream and iVAC will be used as interventions after the implant is placed.

The dosage of indocyanine-green (IC-green) to be used for assessment of mastectomy flaps will be in 10 mg boluses, not to exceed 5 mg/kg.

Nitro-Bid® (nitroglycerin ointment, 2%) at a dose of 45 mg (equal to 7.5 cm on the measuring strip provided with packaging) will be used. The paste will be applied to remnant breast skin after skin closure and surgical dressings placed over top.

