4.1 Primary Outcomes

4.1.1 The primary outcomes will be the following perfusion-related problems:

- Soft tissue ischemia/loss (i.e. partial and full thickness soft tissue defects identified postoperatively in clinic follow up)
- Surgical site infection (i.e. soft tissue cellulitis or abscess identified postoperatively either clinically or with wound culture)
- Delayed wound healing (manifesting as suture dehiscence and opening of an incisional wound)

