5.1 Study Related Activities

Potential subjects will be identified by the physician, advanced practice provider, or research coordinator. This individual will discuss the study with the patient and answer any questions or concerns they may have. This will take place in an exam room, hospital room, or by phone depending on whether or not the patient is inpatient or a clinic patient.

Signed informed consent will be obtained from each subject who will be undergoing mastectomy with immediate breast reconstruction using breast implants during a pre-operative appointment in the General Surgery (Breast Oncology) or Plastic Surgery clinic. After the subject has been identified as meeting the inclusion criteria by the clinician or research coordinator, the study coordinator will obtain the signed informed consent. A signed copy of the consent form will be given to the subject. Once the patient has agreed to take part in the study and sign the consent form, pre-operative photos of the breast will be taken. Pregnancy tests performed 15 days apart (prior to surgery) is done as standard of care for all women of childbearing age potentially undergoing this surgery.

Twenty subjects will be randomized to each arm of the study using sealed instructions provided by the study coordinator who will inform the clinician of the arm prior to surgery. The envelopes will be filled prior to the study with envelopes containing a document indicating to which group the patient will be a part of. The envelopes will be sealed and shuffled and then labeled from subject 1 through 160.

Once the subject is randomized to an arm of the study, the operating surgeon will be informed of the arm prior to the surgery. On the day of surgery, the surgeon will decide intraoperatively whether an implant/tissue expander can be safely placed without compromising perfusion of the flap. If the surgeon determines that an implant/tissue expander cannot be safely placed, they will continue to be followed as that indicates a perfusion related problem. At that point, another envelope will be introduced into the pre-made envelopes with that subject’s assigned arm. Pictures will be take pre-

The Effect of Nitroglycerin Ointment, Fluorescent Angiography, and Incisional NPWT on Mastectomy Skin Flap Perfusion-Related Problems Comprehensive Cancer Center of Wake Forest University (CCCWFU)

PI: [name] IRB #00038262 NCT03716050 Date of Document: 05/07/2019

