operatively, intraoperatively, and at week 1,2,3, and 4 post-operatively. In addition to these pictures, the data collecting sheet will be completed by the physician, advanced practice provider or study coordinator at week 1, 2,3 and 4 post-operatively.

This is not an intent-to-treat trial. In order to ensure that we are able to gather the most information from this study, we want to be able to closely monitor our enrolled subjects and remove any subjects that are non-compliant with their randomized arm. The study coordinator will be responsible for keeping a detailed Excel spreadsheet of the enrolled subjects and their respective arms of the study. If a subject comes off the study prematurely, another envelope will be introduced to the pre-made envelopes with the withdrawn subject's arm – in this way the arms will never be unbalanced.

This study will be monitored by the Cancer Center's Safety and Toxicity Review (STRC) for SAEs and will also be monitored for accrual by the Clinical Research Oversight Committee (CROC) since this is an institutional intervention study. The standard operating procedures for the STRC can be found below in appendix c.

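### A wound condition that prevents or ends the iVAC can lead to removal under section 5.1 in the iVAC groups only, and one such condition, surgical site infection, is a primary outcome

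*Combined protocol and SAP*

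**What the plan says.** Section 3.2.6 excludes "Patients with pre-existing conditions in whom use of incisional negative pressure wound therapy is contraindicated". Its list begins with "those with evidence of surgical site infection (i.e. erythema, purulent drainage), clinical signs of hematoma (i.e. wound swelling, fluctuance, blood drainage" and continues with "history of persistent cancer, exposed blood vessel on site of proposed therapeutic use, or allergy to acrylics and adhesives". It applies to every candidate, whatever the arm, and gives no time of assessment.

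Under section 5.1, consent is taken at a pre-operative appointment, and after randomisation "the operating surgeon will be informed of the arm prior to the surgery". In section 4.0, only groups 3, 4, 7 and 8 receive the dressing; for group 3, "an incisional vacuum-assisted dressing (iVAC) will be placed over the breast incisions after implant placement". It stays on while the patient is in hospital, for at most 4 days.

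Section 4.1 lists as a primary outcome "Surgical site infection (i.e. soft tissue cellulitis or abscess identified postoperatively either clinically or with wound culture".

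Section 5.1 states that the trial does not follow intention to treat and that the team wants to "remove any subjects that are non-compliant with their randomized arm". A subject who leaves early is replaced by a new envelope for the same arm. One retention rule is given: a subject in whom an implant or expander cannot safely be placed continues to be followed, because that counts as a perfusion problem. Nothing comparable covers a subject whose iVAC is not applied or is stopped.

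**The concern.** Three of the five items in 3.2.6 (infection of the surgical site, haematoma, exposed vessel) describe a wound that normally does not exist when the patient is screened and randomised; a recent biopsy or lumpectomy site is the likely exception. In practice these conditions matter when someone is about to place an iVAC or is deciding whether to continue it, and that happens in four of the eight groups.

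If the dressing is then withheld or stopped, the subject has not received her arm as assigned, and section 5.1 allows her to be removed and replaced. A subject with the same early infection in a group without iVAC has departed from nothing, so she stays and her infection is counted. Removal would then depend on the outcome and would act on one side of the iVAC comparison only. Section 8.0 intends these rates to be used in designing a larger trial, so the bias would carry forward.

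**Working it through.** **The plan's own figure.** The point rests on no printed figure, but section 8.3.1 gives the frame: four groups of 20 combined make 80 against 80, which is the size of an iVAC against no-iVAC comparison. Exact binomial enumeration of the two-sided pooled Z test at alpha 0.05, 10% against 30%, gives power 0.90284, as printed. The same enumeration at 10% against 10% gives a false-positive rate of 0.049.

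**Inputs.**
- p, true infection risk, equal in all groups (no iVAC effect): 10%. Section 8.3.1 uses 10% as the anticipated average rate; it is not specific to infection, so its use here is an assumption.
- f, share of infections in the iVAC groups that lead to removal: not in the documents. Assumed range 10% to 50%.
- Removed subjects are replaced in the same arm (section 5.1), and replacements face the same rule.

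**Formula.** Of all subjects randomised to iVAC groups, a fraction pf is removed and p(1 − f) is retained with an infection. The observed rate among those retained is p(1 − f) / (1 − pf). The other groups show p.

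- f = 0.10: 0.090 / 0.990 = 9.1%
- f = 0.25: 0.075 / 0.975 = 7.7%
- f = 0.50: 0.050 / 0.950 = 5.3%

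| f (assumed) | Removed per 80 randomised (80 × p × f) | iVAC groups | Other groups | Spurious difference | False-positive rate, nominal 0.05 |
|---|---|---|---|---|---|
| 0 | 0 | 10.0% | 10% | 0 | 0.049 |
| 0.10 | 0.8 | 9.1% | 10% | 0.9 points | 0.053 |
| 0.25 | 2.0 | 7.7% | 10% | 2.3 points | 0.077 |
| 0.50 | 4.0 | 5.3% | 10% | 4.7 points | 0.190 |

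At p = 20% the same shares give 18.4%, 15.8% and 11.1% against 20%, that is, differences of 1.6, 4.2 and 8.9 points.

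**Single groups.** One removed subject is worth up to 1/20 = 5 points in one arm and up to 1/80 = 1.25 points in the combined iVAC groups.

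**If every subject stays in her randomised group,** f = 0 and this bias is zero, whatever 3.2.6 says.

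**The case against.** The best defence starts from the wording of 3.2.6. It is confined to pre-existing conditions, parallel to 3.2.3 and 3.2.5, and nothing says that eligibility is checked again after randomisation. Applied as written, it drops nobody differentially. That stands in full: the loss comes from the removal rule in section 5.1.

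The removal step is itself partly a matter of interpretation. Section 4.0 sets a maximum time for the dressing and no minimum, so stopping early is not plainly non-compliance. It also says that a subject who needs therapy will be treated, without mentioning removal. Withholding the dressing altogether is the clearer departure, but placement comes at the end of surgery, when a new infection would hardly be evident. These arguments limit how often the problem would arise. They do not close the gap, because the text leaves to the coordinator a decision that depends on the outcome.

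The retention rule for subjects without an implant shows that the plan's authors meant to keep perfusion failures in view. That rule covers implant placement only.

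Finally, this is a pilot, and section 8.3.1 quotes an interval of about ±22.8 points for a group of 20 at an observed rate of 50%; a shift of 2.3 points is small beside that. This is true of single groups. The shift always favours iVAC, however, and a wide interval does not correct it. Sections 8.0 and 8.3.2 promise dropout rates and reasons by group, which could reveal such removals. But 8.3.2 defines attrition as missing the final assessment, so a removed subject who still attends her visits would not count.

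**Conclusion.** The point holds as an interaction between two sections. Section 3.2.6 names wound-level conditions without an assessment time, and section 5.1 permits removal and replacement when the arm is not followed. Together they can take subjects out of groups 3, 4, 7 and 8 for a reason tied to a primary outcome, while the same event elsewhere is counted. The direction is towards a favourable iVAC rate.

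A reader might infer that 3.2.6 itself makes a subject with a postoperative infection ineligible, and so empties the iVAC groups of early infections and haematomas. The documents do not support that. The criterion covers pre-existing conditions in all arms, and a new infection is not pre-existing. Nor is haematoma a primary or secondary outcome; losing such cases matters only through any infection or wound-healing event that goes with them.

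The size is unknown. With 10% true risk in every group and 80 against 80, removing 10% to 50% of iVAC-arm infections produces a spurious difference of 0.9 to 4.7 points. Both the risk and the shares are assumptions. The dressing is in place for at most 4 days, so the low end may be nearer the truth. The remedy is cheap enough to be worth making anyway.

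**What to change.** - **Section 3.2.6:** state that it is assessed before the envelope is opened, identically for all arms.
- **Section 5.1:** state that a subject whose iVAC is not applied or is stopped stays in her randomised group, is followed to day 30, and has all primary outcomes counted. Such a subject is not replaced on that ground.
- **Data sheet:** record the same wound conditions in all eight groups, and in the iVAC groups whether the dressing was applied and when it was removed.
- **Sections 3.2.6 and 4.0 (Study Risks):** reconcile the two lists of contraindications to negative pressure therapy. Both name exposed vessels, but infection and haematoma appear only in 3.2.6. Which conditions should affect use of the dressing is for the investigators to settle.

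The cost is a few sentences and a small addition to the data sheet. The downside is modest: the iVAC rates may look less favourable, and they will include some subjects who did not receive the full dressing.

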3.3 Inclusion of Women and Minorities

Females of any race or ethnicity who meet the above-described inclusion criteria are eligible to participate in this study.

The Effect of Nitroglycerin Ointment, Fluorescent Angiography, and Incisional NPWT on Mastectomy Skin Flap Perfusion-Related Problems Comprehensive Cancer Center of Wake Forest University (CCCWFU)

PI: [name] IRB #00038262 NCT03716050 Date of Document: 05/07/2019

4.0 Study Outcomes and Study Measures

We will perform a randomized pilot study comprised of eight groups. All of these groups employ accepted techniques, medications and dressings and therefore are not experimental.

Group 1: Breast skin after mastectomy will be clinically examined by the surgeon to determine if there is adequate blood flow to the skin to allow safe coverage of the breast implant. No dye study, ointment, or vacuum dressing will be applied to the breast after implant placement.

Group 2 - Breast skin after mastectomy will be clinically examined by the surgeon, and nitroglycerin (NTG) cream will be applied to the breast skin after implant placement. This cream does not have systemic effects but may improve blood flow to the remnant breast skin after mastectomy.

Group 3 - Breast skin after mastectomy will be clinically examined by the surgeon, and an incisional vacuum-assisted dressing (iVAC) will be placed over the breast incisions after implant placement, which may improve blood flow to the skin and help wound healing.

Group 4 - Breast skin after mastectomy will be clinically examined by the surgeon, and both NTG cream will be applied to the breast skin and an iVAC will be placed over the incisions after implant placement.

Group 5 - Blood flow to breast skin after mastectomy will be examined using a fluorescent dye study called fluorescent angiography (FA) to determine if there is adequate blood flow to the skin to allow safe coverage of the breast implant. No further intervention will be used after implant placement.

Group 6 - Blood flow to breast skin breast skin will be examined using FA, and NTG cream will be applied to the skin after the implant is placed.

Group 7 - Blood flow to breast skin breast skin will be examined using FA, and an iVAC will be placed over breast skin incisions after the implant is placed.

Group 8 - Blood flow to breast skin breast skin will be examined using FA, and both NTG cream and iVAC will be used as interventions after the implant is placed.

The dosage of indocyanine-green (IC-green) to be used for assessment of mastectomy flaps will be in 10 mg boluses, not to exceed 5 mg/kg.

Nitro-Bid® (nitroglycerin ointment, 2%) at a dose of 45 mg (equal to 7.5 cm on the measuring strip provided with packaging) will be used. The paste will be applied to remnant breast skin after skin closure and surgical dressings placed over top.

Incisional negative pressure wound therapy will consist of a standard sponge dressing with adhesive drape, either Ioban® 2 (3M™) or KCI-V.A.C.® Drape (KCI®), to continuous suction at 125 mm Hg while the patient is in hospital and not to exceed 4 days.

A physician will see the subjects on a regular weekly basis for up to 30 days once the procedure has been completed. These clinical visits are standard of care and the subject's health and well-being will be monitored rigorously during these visits. If during any of these visits, the physician deems a therapy necessary to prevent impairment/damage and improve well-being, the subject will be treated appropriately.

The Effect of Nitroglycerin Ointment, Fluorescent Angiography, and Incisional NPWT on Mastectomy Skin Flap Perfusion-Related Problems Comprehensive Cancer Center of Wake Forest University (CCCWFU)

PI: [name] IRB #00038262 NCT03716050 Date of Document: 05/07/2019

At no point during this study will the needs of the randomized arm/research take priority over the subject's health and well-being.

Study Risks

Risks of surgery may include bleeding, infection, hematoma/seroma formation, risks of anesthesia, implant/tissue expander failure, extrusion, or tissue necrosis.

Risks with ICGLA may include a potential risk for anaphylaxis/urticarial reaction. Caution must be taken with patients with iodine/iodinated contrast allergy. There have been no studies performed to evaluate carcinogenicity, mutagenicity, or impairment of fertility.

Risks associated with the use of nitroglycerin paste may include dizziness, light-headedness, blurred vision, fainting, increased risk of alcohol toxicity if consumed in conjunction with nitroglycerin use, headaches, severe allergic reactions (rash, hives, itching, difficulty breathing, tightness in chest, swelling of mouth, face, lips, throat or tongue), flushing and red, swollen, blistered or peeling skin.

Vacuum-assisted closure is routinely used in the medical setting for various types of traumatic, surgically-created, or chronic wounds. The use of NPWT therapy is contraindicated when the system is in direct contact with vital structures (i.e. exposed vessels, anastomoses, organs, or nerves), or when the following are present in the wound: malignancy, untreated osteomyelitis, non-enteric and unexplored fistulas, or necrotic tissue with eschar present. Use of Ioban® drape is contraindicated in patients with a known sensitivity to iodine. In these instances, the KCI-V.A.C.® drape will be used. Patients with known allergy to acrylics or adhesives may develop an adverse hypersensitivity reaction to the KCI drape and will be excluded from the study.

